Brain regions implicated in Autism: Several studies aiming to identify the etiology of autism have indicated involvement of limbic system structures including the amygdala, hippocampus, & the ACC⁴¹⁻⁴³. These limbic structures also show a high affinity for NMDA receptor binding. ACC: is functionally associated with information processing and response to emotional cues and is, therefore, a region of interest in autism. The ACC also has close anatomic connections to the amygdala & participates in emotional regulation. Lesions of ACC are known to cause blunted affect, disinhibition, disabling repetitive behaviors, & impaired social judgment including the inability to interpret social cues⁴⁴. Converging evidence from various investigative modalities suggests abnormalities in the ACC region in individuals with ASD including histopathological changes of increased cell packing density & decreased cell size, smaller in volume, decrease in regional cerebral blood flow, & metabolically less active^{34-35, 38, 39-40} with abnormal functional activity (theory of mind task related & resting state)⁴⁵⁻⁵². MTL: structures, the hippocampus & amvadala, play crucial roles in associative memory & social cognition, respectively, & lesions in the MTL are implicated in social impairments intrinsic to ASD⁵³⁻⁵⁵. Converging evidence of abnormalities in the MTL in ASD comes from various histopathological & imaging studies revealing decreased neuronal size and increased cell density and cytoarchitectural minicolumnar pathology, bilateral decreased volume & hypo-perfusion, and abnormal activation especially of amygdala on face recognition41,45-46,48, 55-65.

II. SPECIFIC AIMS

Primary Aims

Aim 1) To examine the clinical efficacy & tolerability of memantine for the treatment of social impairment in youth with ASD. We will study the short- & long-term clinical effects of memantine in 40 children and adolescents with ASD by conducting a 12-week randomized-controlled trial (RCT).

Aim 2) To examine the effect of memantine therapy on neural function in youth with ASD. We will assess neural response to memantine therapy by measuring spectroscopic

& resting state functional connectivity (RsFc) changes with memantine treatment. We will also assess association of neural & clinical response to memantine therapy.

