Contraindications to MR scanning—braces, metal in the body, participant refusal to scan (e.g., due to severe anxiety or claustrophobia), etc.—are exclusionary for the scanning component of the trial. Subjects are allowed to have a security object (ei. ball or blanket) that is MR-safe and screened, in the scanner to help with possible anxiety they might experience due to the scanning. Healthy control subjects with contraindications to MR scanning will not be eligible to participate in the trial. However, in the event that an ASD subject with MR scanning contraindications otherwise meets all inclusionary criteria and does not meet any additional exclusionary criteria, that subject will be eligible to participate solely in the 12-week randomized-control phase of the study.

V. SOURCE OF SUBJECTS

We propose to enroll up to 60 subjects with ASD and 30 healthy controls for a total of 90 subjects. Up to 60 children and adolescents with ASD who exhibit marked social impairment will be enrolled in order to randomize 40 eligible subjects. In addition, up to

30 children and adolescents with no history of major psychiatric disorders, including ASD, will enroll in order for 20 eligible age-, sex-, & IQ-matched subjects to participate as neuroimaging healthy controls. Subjects will be recruited from the referral pool of existing and new patients at three different MGH sites – the Bressler Program for ASD, the Lurie Center for Autism, & the child psychiatry outpatient clinic – and from the general public by flyers and internet advertisements. Individuals who respond to local advertising will be screened for eligibility first by the study coordinator over the phone using an IRB-approved script prior to enrollment.

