Participating children and adolescents with ASD who meet the eligibility criteria will be randomly assigned to either memantine or placebo for the course of the 12-week RCT. Subjects will be assessed weekly during the titration phase (Weeks 1-4) & during the maintenance phase at midpoint (Week 6), Week 9, & at completion (Week 12/early termination). The same caretaker (a parent/guardian most familiar with the subject's day-to-day behavior) will participate in the assessment of behavioral symptoms at all visits of the treatment phases.

Randomization: The MGH Clinical Trials Pharmacy will prepare the blinded

memantine and placebo capsules for the study. ASD subjects will be randomized to either active memantine or placebo in a 1:1 ratio after they have been determined to meet all eligibility criteria. Randomization lists stratified by gender and racial/ethnic minority status (minority vs. Caucasian) will be generated by the statistician & passed to the investigational pharmacy for assignment.

Washout Period: ASD subjects who are currently being treated with prohibited psychotropic medications as listed in the exclusion criteria must discontinue the use of their medication to be eligible for participation in this study. Medication washout is recommended by our clinicians to participants, their parent/guardian, and current providers – this is done based on a case-by-case assessment, considering the duration on drug, the dose, and the adverse effects associated with the treatment and effects of stopping that medication/treatment. Our office does not take over care for the patient, but remains available during this time period. The washout schedule –which will span two weeks or more -- will be discussed with the participant, their parent/guardian, and current providers. Individuals taking a medication that is effectively and safely treating their symptoms will not be taken off of such medication for the purpose of enrolling in this study.

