After the 2D-JPRESS dataset is resolved into a series of one-dimensional spectra where each spectrum is modeled and fitted with GAMMA simulated J-resolved basis sets, Glu levels will be derived from the total integral across the J-series. Glu transverse relaxation time (T2) will be obtained from the raw peak vs. TE decay curve fitted with

Levenberg-Marquardt algorithm using an exponential decay function (for Glu T2) convoluted with a polynomial function (for Glu J-coupling) that will be obtained from the GAMMA simulation run with previously measured spectral parameters. Data quality will be assessed by LCModel calculated Full Width Half Maximum (FWHM), Signal to Noise Ratio (SNR) and Cramer-Rao Lower Bounds (CRLB).

The following brain measures will be examined between groups and withinsubject across time (e.g., pre- versus post-treatment and correlations between the measures of brain activity and clinical features):

1) ¹HMRS measures of brain Glu in:

a) ACC

b) MTL

2) measures of resting state functional connectivity of:

- a) dorsal & ventral ACC with prefrontal cortex including VMPFC;
- b) bilateral amygdala with insula & VMPFC;

c) bilateral hippocampus with posterior cingulate cortex.

Pretest-posttest brain activity differences will be analyzed using linear regression models, where treatment group is the primary predictor and pretest measures of brain activity are covariates. A general linear regression model will evaluate the difference between the treatment groups in posttest brain measures while controlling for each subject's pretest measures of brain activity. This approach is equivalent to analyses of covariance (ANCOVA). We will also test if changes in Glu in memantine and placebo (PBO) responders differ from changes in Glu over time in healthy controls (HCs). This requires a three-group comparison: memantine responders vs. PBO responders vs. HCs. We will use a GLM to compare Glu changes from baseline to endpoint. If the direction and magnitude of change among the three groups are the same, there will be no group by time interaction. If the interaction is significant and responders show greater changes compared to HCs, it will indicate that the changes observed in responders are greater than expected from normal changes in Glu activity. We will do follow-up tests to separately test the interactions for each pair of the three groups analyzed.

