We also predict normalization of brain activity measures with memantine treatment. "Normalization" will be defined as having achieved a resting state functional connectivity level that is no more extreme than the 95th percentile of the control distribution. Normalization ratings between the memantine and PBO groups will be compared using a logistic RMs. A significant effect would mean an increased likelihood of normalization in memantine-treated subjects.

To test our hypothesis of a significant association between neural and clinical response and between glutamate and functional connectivity response, we will use endpoint clinical efficacy scores as the dependent variable and change in brain activity measures from baseline to endpoint as the independent variables. For our exploratory hypothesis examining neural biomarkers of response to memantine therapy, we will use a GLM with endpoint clinical efficacy scores as the dependent variable, baseline brain activity measures as the independent variables, and baseline clinical scores as a covariate.

Resting state data will be analyzed using a seed driven approach with custom software (Conn)⁸⁸. Data will be slice time corrected, realigned, coregistered, normalized, and spatially smoothed as necessary. Physiological & other spurious sources of noise

will be estimated using the CompCor method, and removed together with movementrelated covariates. The residual BOLD time-series will be band-pass filtered over a lowfrequency window of interest (0.009Hz<f<0.08Hz). Correlation maps will be produced by extracting the residual BOLD time course from bilateral anatomically defined amygdala (WFU_Pickatlas) seed regions, and computing Pearson's correlation coefficients between that time course and the time course of all other voxels. Correlation coefficients will be converted to normally distributed scores using Fisher's transform to allow for second-level General Linear Model analyses. Between group differences will be calculated for each ROI.

Power Considerations

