Spectroscopic: For our preliminary data from 7 ASD and 7 HC subjects, our significant finding (paired t-test, p =0.01) of 31% higher Glu levels in the ACC of ASD subjects compared to HCs was determined to have a large effect size of d=1.20 with an associated power= 0.55. Left MTL data produced an effect size d=1.03 with power = 0.43. Right MTL data produced an effect size d=1.15 with power =0.51. Assuming we observe the same sampling variability in the proposed study, we have greater than 90% power with a large effect size of d=1.10 to detect a 15% decrease in Glu in the ASD group with treatment.

Functional: In our preliminary studies (ASD: N=17; HC: N=16) of resting state functional connectivity with the bilateral amygdalae seeds, we found significant hyperconnectivity of the ASD group compared to the HC group (e.g., with the insula, p<0.0001 FWE cluster level corrected), and based on the preliminary data, power will be at 95% to detect between-group differences between the proposed ASD (N=40) and HC groups (N=20).

VII. RISKS AND DISCOMFORTS

Risks of Taking Memantine:

The most frequently observed adverse reactions with memantine are dizziness, confusion, headache, constipation, hypertension, cough, pain, hallucinations, somnolence, vomiting, dyspnea, and fatigue. Serious adverse reactions include Stevens-Johnson syndrome and seizures. All participants will be closely monitored for serious adverse reactions and drug-drug interactions with their ongoing concomitant medications. All serious unexpected adverse experiences of a research subject will be reported to the Partners Human Research Committee.

Problems and side effects not listed above and not known at this time could occur. Subjects will be told of any changes in the way the study will be done and any newly discovered risks to which they may be exposed.

Risks of Blood Draws:

When blood is drawn, some discomfort may be associated with it at the time of the blood draw. Bruising and/or bleeding at the needle site may occur. Occasionally a person feels faint. Rarely, an infection may develop. If an infection does occur, it can be treated. A topical anesthetic cream (Topicaine, EMLA, or ELA-MAX) will be applied to numb the skin where blood will be drawn if subjects prefer.

Risks of ¹HMRS:

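### The neural-clinical association model has no treatment term and no stated analysis population; if both arms are analysed together, separate drug effects on brain and behaviour can appear as a neural-clinical link

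*Combined protocol and SAP*

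**What the plan says.** Aim 2 (II. Specific Aims, under Primary Aims) includes this intention: "We will also assess association of neural & clinical response to memantine therapy". The matching model is in VI. Biostatistical Analysis, Neuroimaging Data Analysis. Its outcome is given as "we will use endpoint clinical efficacy scores as the dependent variable", and its predictors are "change in brain activity measures from baseline to endpoint as the independent variables". Nothing else is listed: no treatment term, no baseline clinical score and no analysis population.

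Other models in the same chapter are fuller. The clinical GEE under Clinical Data Analysis includes treatment group, visit and their interaction. In the pre/post brain model, "treatment group is the primary predictor and pretest measures of brain activity are covariates". The comparison of normalization rates is between memantine and placebo. The exploratory biomarker model, described straight after the association model, uses "baseline brain activity measures as the independent variables, and baseline clinical scores as a covariate".

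**The concern.** The trial is designed in the expectation that memantine changes both glutamate and social impairment. If it does, arm is a common cause of the predictor and the outcome in the association model. The memantine group then sits apart from the placebo group on both axes, and a line through the combined cloud has a slope even when subjects with larger brain change do no better than others in the same arm.

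A significant slope would be read as evidence that clinical response tracks neural response from person to person. In the situation just described it would only restate the two treatment effects that the clinical GEE and the pre/post brain model already test. The more the drug does on both measures, the larger the artefact.

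**Working it through.** **Inputs from the plan**
- Randomised ASD subjects: up to 60 are "enrolled in order to randomize 40 eligible subjects" (V. Source of Subjects).
- Allocation: "randomized to either active memantine or placebo in a 1:1 ratio" (12-Week RCT, Randomization), so 20 per arm.
- Brain effect: "a large effect size of d=1.10 to detect a 15% decrease in Glu in the ASD group with treatment" (Power Considerations).
- Preliminary data: ACC Glu 31% higher in ASD than in controls, d=1.20, 7 v 7 (Power Considerations).

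**Inputs assumed, because the plan does not give them**
- Clinical effect: 0.3, 0.5, 0.8 and 1.0 SD.
- Test: two-sided 5%.
- Outcome: continuous and normal.
- Within-arm association: none. This is the null being tested.
- Subjects with paired scans: 20 per arm, then 15 and 10, because scan-ineligible ASD subjects may still be randomised (III. Length of Study; IV. Subject Selection Criteria).

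**Step 1: reproduce the plan's figure.** With d=1.10 and 20 per arm, the noncentrality is 1.10 × √(20/2) = 3.48. Power is Φ(3.48 − 1.96) = 0.936 by the normal approximation and 0.924 by the noncentral t. The stated power of more than 90% is reproduced if d=1.10 is read as a memantine v placebo contrast.

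**Step 2: a smaller brain effect from the plan's own preliminary figures.** If 31% of the control mean is 1.20 SD, a 15% fall from the ASD level is 0.15 × 1.31 = 0.1965 of the control mean. That equals 0.1965 / 0.31 × 1.20 = 0.76 SD.

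**Step 3: induced correlation.** For equal arms, unit within-arm SDs and no within-arm association,

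r = 0.25·d_b·d_c / √[(1 + 0.25·d_b²)(1 + 0.25·d_c²)].

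Example: d_b = 1.10 and d_c = 0.8 give 0.22 / √(1.3025 × 1.16) = 0.22 / 1.229 = 0.179.

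**Step 4: rejection rate of the brain-change slope.** Each cell has 40,000 simulated trials with 20 per arm. Brain change = d_b·T + noise and endpoint score = d_c·T + independent noise, where T is 1 for memantine and 0 for placebo. The slope is tested by ordinary least squares.

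| Clinical effect (SD) | Glu 1.10: r | Glu 1.10: rate, no arm term | Glu 0.76: r | Glu 0.76: rate, no arm term |
|---|---|---|---|---|
| 0 | 0 | 5% | 0 | 5% |
| 0.3 | 0.07 | 7% | 0.05 | 6% |
| 0.5 | 0.12 | 11% | 0.09 | 8% |
| 0.8 | 0.18 | 20% | 0.13 | 13% |
| 1.0 | 0.22 | 27% | 0.16 | 17% |

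With arm in the model, the rate is 4.8% to 5.2% in every cell. A zero brain effect also leaves the rate at about 5%, whatever the clinical effect.

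**Step 5: fewer paired scans.** With Glu d=1.10 and clinical effects of 0.3, 0.5 and 0.8 SD, the rates without an arm term are about 6.6%, 9.3% and 16% at 15 per arm, and 6.1%, 7.5% and 11.8% at 10 per arm.

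**The case against.** Five points can be made for the plan.

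1. **Pooling is not stated.** Aim 2 speaks of response to memantine therapy, which can mean memantine-treated subjects only. That analysis would have no confounding by arm, and an arm covariate would be constant. This stands as a limit on the finding. But the model as listed carries no such restriction, and the same section analyses placebo responders, so the population has to be stated either way.

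2. **The hypothesis is only called an association.** If the drug moves both measures, a pooled association does exist in the trial population, and the rates above are error rates only against a null of no within-arm link. This stands too. The problem is that the listed model cannot tell a link between individuals from two separate drug effects.

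3. **The d=1.10 may not be a between-arm effect on change.** Power Considerations describes a fall in the ASD group and borrows its variability from a cross-sectional comparison. This is why 0.76 SD is shown alongside.

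4. **The simulation is narrow.** It has one normal outcome and one predictor. CGI-I as an ordinal or binary outcome, and several brain measures together, were not simulated.

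5. **The association is secondary within Aim 2.** It is not the primary efficacy test. That bears on priority, not on whether the model is adequate.

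**Conclusion.** The point holds as a conditional one. The association model is listed without a treatment term or a population. If it is fitted to both arms, its slope mixes any within-arm link with the drug's separate effects. At 20 per arm, over assumed clinical effects of 0.3 to 1.0 SD, the rejection rate against a null of no within-arm association runs from about 7% to 27% with Glu d=1.10, and from about 6% to 17% with Glu d=0.76. It is lower with fewer scanned subjects. These figures rest on the normal, single-predictor, two-sided 5% set-up described above.

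A reader might infer that the plan definitely pools the arms, or that the false-positive rate is generally 2 to 5 times nominal. The documents support neither. The population is left open. No clinical effect size is given, so no single multiple can be quoted: at 0.3 SD with Glu d=1.10 it is about 1.4 (7.2% / 5%), and if either drug effect is zero it is 1. Nor can it be said that the Aim 2 hypothesis goes untested, since a memantine-only analysis would avoid the problem.

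The change should be made before the data are analysed. It does not affect the primary efficacy analysis.

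**What to change.** In Neuroimaging Data Analysis, state that the association model uses all randomised ASD subjects with paired scans, and add treatment arm as a covariate so that the tested slope is the within-arm association. Report the slopes for memantine and placebo separately as descriptive results, and show any unadjusted pooled correlation only as a descriptive figure. If the analysis was meant for memantine subjects only, say that instead; it would then rest on at most about 20 subjects.

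The cost is one sentence, one degree of freedom and some loss of precision. Between-arm variation in brain change no longer contributes to the slope; at d=1.10 that is 0.25 × 1.10² / (1 + 0.25 × 1.10²) = 0.3025 / 1.3025, or about 23% of its variance. No new data are needed.

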Autism spectrum disorder (ASD) is a neurodevelopmental disorder characterized by difficulties with socialization & reciprocal communication, along with restricted, repetitive behavior¹. An increasingly higher prevalence of ASD is documented in each successive epidemiological survey and is now estimated to affect more than 1% of youth². Social Deficits in Autism: Deficits in social interaction are the central feature of autism and often result in significant impairment in cognitively capable individuals with ASD. In light of the growing recognition of ASD in intellectually capable individuals of all ages, there is an acute need for effective treatment for social deficits. Although there are drugs proven to be effective in treating target symptoms of hyperactivity, irritability, & repetitive behaviors in ASD, to date, no medications have consistently been shown to reliably improve social impairments in ASD³⁻⁸. Earlier studies of fenfluramine, secretin, & naltrexone have largely been disappointing⁹⁻¹². Emerging evidence on the safety & efficacy of glutamatergic agents for the treatment of social deficits in ASD is encouraging. **Glutamatergic Dysregulation in Autism:** Glutamate (Glu) is the primary excitatory amino acid neurotransmitter in the brain. Glu, through its activity at N-methyl-D-aspartate (NMDA) receptors, is crucial for neurodevelopmental processes, including neuronal plasticity & higher cognitive functioning¹³. Over-activation of Glu is associated with excitotoxicity & apoptosis. Dysregulation in glutamatergic activity has been hypothesized to contribute to the pathophysiology of ASD¹⁴⁻¹⁵. Evidence for increased Glu activity in autism comes from serological, postmortem brain, and preliminary genetic studies¹⁶⁻²⁴. ¹HMRS in autism provides *in vivo* evidence of abnormal glutamatergic brain activity in autism by quantifying Glu levels in combination with glutamine (Gln) & gammaaminobutyric acid (GABA; Glu+Gln+GABA=Glx). Although no Glx abnormality was identified in the temporal lobes or anterior cingulate cortex (ACC) by 1.5 T ¹HMRS in preschool-age children with ASD lower levels of Glx were observed in grev matter by 3T ¹HMRS in older school-age children with ASD²⁵⁻²⁷. On the contrary, in adults with ASD, Glx levels are found to be higher in the amvadalo-hippocampal region (on 1.5 T ¹HMRS) and decreased in the right ACC (on 3T ¹HMRS)²⁸⁻²⁹. More recently, Harada & colleagues³⁰ specifically examined Glu metabolites at 3T ¹HMRS in children with ASD and noted no abnormality in Glu levels in the frontal lobe & lenticular nuclei. Taken together, previous ¹HMRS studies in autism suggest Glx dysregulation in various regions, including regions implicated in autism (i.e., medial temporal lobe [MTL] & ACC). Our ¹HMRS study in adolescent males with high-functioning ASD (HF-ASD) suggest significantly increased Glu in the ACC with no change in the bilateral MTL regions³¹. Role of Glutamate Modulators in the Treatment of Autism: Glutamatergic agents lamotrigine, amantadine, & D-cycloserine have been studied as potential treatments for symptoms of ASD. Lamotrigine attenuates Glu release by inhibiting voltage-sensitive sodium channels in the presynaptic neuronal membranes³². In a randomized-controlled trial (RCT) of lamotrigine in 28 children with ASD, although there was marked improvement in autism behaviors, an equally robust response to placebo (PBO) resulted in the lack of a statistically significant separation between the two groups³³. Amantadine, an antagonist at NMDA receptors, has also been studied in ASD. In a RCT of amantadine in 39 youth with ASD, amantadine was well tolerated and although

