- CGI- ASD- Social Interaction.
- CGI- ASD– Mannerisms.
- CGI- ASD– Social Communication.
- MGH ASD Symptom Checklist (MGH-ASD-SCL): The spectrum of ASD symptoms will be screened by using clinician administered MGH-ASD-SCL. This screening instrument adopted items from DSM-5 diagnostic criteria for ASD and assesses for the individual core domains and associated features of ASD.
- Social Emotional Competence Scale–Clinician Rated (MGH-SEC-S-C): This is a 37item scale that assesses social competence and abilities in relation to ASD on a Likert scale from 0 to 8.

Level of Functioning

• DSM Global Assessment of Functioning Scale (GAF)⁷⁶: a composite rating of an individual's overall level of functioning (1= worst to 100 = best).

Safety

- Adverse Experiences: to record any adverse health events experienced during the study, along with duration, severity, cause, treatment, and outcome.
- Concomitant Medications: to record additional medications taken during the study.

VI. BIOSTATISTICAL ANALYSIS

Clinical Data Analysis

Because this is a RCT following subjects over a short period of time, missing data are not expected to impact our analyses such that standard statistical tests will be employed. Changes in the primary outcome measures of efficacy (CGI-I & SRS-2) within & between study groups over time will be tested with longitudinal generalized estimating equation (GEE) regression models (RM) estimated using STATA 12.0 within the framework of the general linear model (GLM). For binary outcomes, logistic RMs will be fit with the binomial family & the logit link. For count data, Poisson RMs will be fit with the Poission family & the log link, for normally distributed data, linear RMs will be fit with the Gaussian distribution & identity link. Each model will predict outcome scores from treatment group (memantine vs. PBO), study visit (ordinal predictor), & the group by visit interaction, which is our test of efficacy. Secondary outcome measures (ABC-SW, GAF, ADHD-SCL, CY-BOCS-PDD, CDRS-R, CASI-Anx, & SAICA) will be examined using models similar to the primary outcome measures. Changes in the tolerability outcome measurements will be tested using Chi-squared tests. All analyses will be intention to treat (ITT).

Neuroimaging Data Analysis

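### The exploratory model for brain markers of memantine response has no arm or arm-by-marker term, so it cannot tell a marker of drug response from a prognostic marker

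*Combined protocol and SAP*

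**What the plan says.** Section VI (Biostatistical Analysis), Neuroimaging Data Analysis, introduces the analysis with "For our exploratory hypothesis examining neural biomarkers of response to memantine therapy". The model follows: "we will use a GLM with endpoint clinical efficacy scores as the dependent variable, baseline brain activity measures as the independent variables". The one adjustment variable is the subject's clinical score at baseline. That is the full list of terms. The text does not say whether both randomised arms or only memantine subjects are analysed.

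The preceding sentence, on the association between neural and clinical response, has the same outcome and uses "change in brain activity measures from baseline to endpoint as the independent variables". It lists no arm either.

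Elsewhere the plan does name arm:
- In the pre/post brain comparison: "where treatment group is the primary predictor and pretest measures of brain activity are covariates".
- In the clinical efficacy models: "Each model will predict outcome scores from treatment group (memantine vs. PBO), study visit (ordinal predictor), & the group by visit interaction".
- In the normalization comparison, which sets memantine against placebo.

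None of these supplies the missing terms. The first has a brain measure as outcome, the clinical models contain no brain marker, and the third compares rates of normalized connectivity.

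**The concern.** A marker of response to a drug is a baseline feature that predicts how much the drug changes the outcome. In a randomised trial, that is a difference between arms in the slope of outcome on marker. A prognostic marker predicts the outcome whatever the treatment. A regression with no arm term estimates one slope, and that slope can be non-zero for either reason.

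The plan's own background shows that improvement without active drug is a live issue in this field. In an earlier trial of a glutamatergic agent in 28 children with ASD, "an equally robust response to placebo (PBO) resulted in the lack of a statistically significant separation between the two groups". This is a group-level result. It does not show that brain measures predict placebo improvement, but it shows that there is placebo improvement to predict.

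At stake is the label put on the finding. A marker of who improves anyway could be reported as a marker of who benefits from memantine, and a true marker of drug response could be missed. The placebo arm that would separate the two is already in the trial, and the model as written makes no use of it for that purpose.

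**Working it through.** **Inputs from the documents.** Target of 40 randomised ASD subjects (Source of Subjects); 1:1 allocation (Randomization), so 20 per arm. ASD subjects who cannot be scanned may still join the randomised phase (Length of Study; Subject Selection Criteria), so the number with brain data can be below 40 and is not given.

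**Assumptions.** The plan gives no sample size, alpha or effect size for this model, so there is no stated figure to reproduce. I take a two-sided 5% test. That matches the plan's practice elsewhere: a two-sided two-sample t test with 7 per group gives power 0.54, 0.43 and 0.51 at d = 1.20, 1.03 and 1.15, against 0.55, 0.43 and 0.51 under Power Considerations. Marker strength is a partial correlation r with the endpoint score given the baseline score, varied over a range. I show n=40 and, as an illustration, n=30 scanned.

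**Step 1: what the slope estimates.** Let

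endpoint = a + c·baseline + t·arm + bP·marker + bI·arm·marker + error,

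with arm = 1 for memantine and 0 for placebo. bP is the prognostic effect and bI the marker-dependent drug effect. Randomisation makes the marker independent of arm, so:
- both arms pooled, no arm term: slope = bP + 0.5·bI
- memantine arm only: slope = bP + bI
- model with arm and arm-by-marker: interaction coefficient = bI

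Simulation agrees. With bP = 0 and bI = 0.5, the mean slopes were 0.25 pooled and 0.50 in the memantine arm.

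**Step 2: a purely prognostic marker (same r in both arms, bI = 0).** The written model's test is t = r·√(n−3)/√(1−r²) on n−3 degrees of freedom. Hand check at r = 0.4:
- n = 40: 0.4 × 6.08/0.917 = 2.65 against a critical value of 2.03, so power is about Φ(0.62) = 73%.
- n = 20: 0.4 × 4.12/0.917 = 1.80 against 2.11, about Φ(−0.31) = 38% (simulated 40%).

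Simulated rates of p<0.05:

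| Subjects scanned | Fit | r=0.3 | r=0.4 | r=0.5 |
|---|---|---|---|---|
| 40 | pooled | 46% | 73% | 91% |
| 40 | memantine arm only (20) | 23% | 40% | 62% |
| 30 | pooled | 35% | 59% | 81% |
| 30 | memantine arm only (15) | 18% | 30% | 48% |
| 40 or 30 | arm-by-marker test | about 5% | about 5% | about 5% |

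**Step 3: the opposite error.** Take r = +0.4 on memantine and −0.4 on placebo, n = 40. On a unit-variance scale bP = −0.4 and bI = 0.8, so the pooled slope is −0.4 + 0.5 × 0.8 = 0. The pooled model flags the marker in about 7% of trials, the interaction test in about 70%.

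**Step 4: what the right test can detect.** Take r on memantine and 0 on placebo:

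| Subjects scanned | r=0.3 | r=0.4 | r=0.5 | r=0.6 |
|---|---|---|---|---|
| 40 | 15% | 22% | 32% | 47% |
| 30 | 12% | 17% | 24% | 36% |

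These rows take equal total variance in the two arms given the baseline score. The 47% at r = 0.6 moves between about 46% and 56% under other residual-variance assumptions. Put another way, the standard error of the interaction slope is about √(4/n) residual SD per marker SD. At n = 40 that is 0.316, and 80% power needs a slope difference of about 0.91. At n = 30 it is 0.365, and the difference needed is about 1.06.

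**The case against.** **The analysis is exploratory.** The plan says so, and no primary conclusion depends on it. This stands, and it limits the weight of the point. But the exploratory label concerns strength of evidence. A larger sample would make this slope more precise without making it answer the stated question.

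**The missing terms could be shorthand, or the intention-to-treat statement could imply both arms.** That statement sits under Clinical Data Analysis and adds no model term. Even if it settles the population, the result is the pooled slope, which still mixes the two effects. The neighbouring models show that the plan names arm where it means to use it.

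**The interaction test is weak here.** This also stands. At r = 0.3 to 0.5 its power is about 15 to 32% with 40 scanned, and a non-significant result would say little. The arm-specific slopes with their intervals are therefore the more useful output.

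**A stronger reading is tempting:** that the model finds only subjects who improve spontaneously or on placebo, and cannot find memantine responders. The documents do not support that. The slope contains half or all of any true interaction. A marker with no prognostic effect (r = 0.6 on memantine, 0 on placebo) is flagged in about 47% of pooled fits and 80% of memantine-only fits at n = 40. The model can pick up such a marker. It cannot show that this is what it picked up.

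**Conclusion.** The point holds in this form: the model as written cannot separate a marker of memantine response from a prognostic marker, whichever population is used, and no other part of the plan repairs this. For a purely prognostic marker with r between 0.3 and 0.5, the chance of a significant result is about 46 to 91% pooled and 23 to 62% in the memantine arm with 40 scanned (35 to 81% and 18 to 48% with 30), where a valid test would give about 5%. These rates rest on assumed correlations, a two-sided 5% level and one marker tested at a time.

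Mislabelling could follow; that it would is inference, since the plan does not say how the result will be reported. A reader should not carry the point over to the primary efficacy analysis, which has its own model with arm in it. The change should be made before analysis, but the trial's main conclusion does not turn on it.

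**What to change.** Replace the model sentence with one that:
- states that all scanned subjects from both randomised arms are analysed;
- fits endpoint clinical score on baseline clinical score, arm, baseline brain measure and arm-by-brain-measure;
- makes the interaction the basis for any claim of a memantine-response biomarker;
- reports the slope in each arm, and their difference, with confidence intervals;
- says that a slope from a model without arm will not be called a marker of memantine response.

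Adding arm as a main effect alone is not enough, because the marker slope would still be averaged over the arms. The neighbouring model on change in brain measures should also say which arms enter and whether arm is included.

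The cost is one or two sentences, with no new data, visits or procedures. The price is precision: with 40 or fewer scanned, only large interactions are detectable. The plan should therefore call the result hypothesis-generating and say that a non-significant interaction is not evidence of no effect.
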